6.5. Safety reporting to Health Authorities and Ethics Committees	26
7. Statistics	26
7.1. Definition of primary endpoint	26
7.2. Justification of number of trial subjects	27
7.3. Description of statistical methods	27

7.4. Description of data management	27
8. Duties of the investigator.....	28
8.1. Investigator's confirmation	28
8.2. Damage coverage	29
8.3. Project management.....	29
9. Ethical considerations	29
9.1. Independent Ethics Committee (IEC).....	29
9.2. Evaluation of the risk-benefit ratio.....	30
9.3. Subject information and consent.....	30
9.4. Subject Confidentiality	30
9.5. Subjects requiring particular protection	31
10. Quality control and quality assurance	32
10.1. Monitoring and auditing.....	32
10.2. Access to data, handling of data and samples (data protection), archiving (place, duration) and destruction	32
10.3. Data entered directly in the Case Report Form (CRF) – definition of source data	33
11. Dissemination of results and publication	33
12. References	34
Appendix 1:	38
[name], administrative director Swiss TPH (Signature).....	Error!
Bookmark not defined.	

Abbreviations

AE: adverse event

CI: confidence interval

CR: cure rate

CRF: case report form

DALYs: disability-adjusted life years

EMA: European Medicines Agency

EPG: egg per gram

ERR: egg reduction rate

GCP: Good Clinical Practice

HB: haemoglobin

ICH: International Council for Harmonisation

IEC: independent ethics committee

MDA: mass drug administration

PCR: polymerase chain reaction

PHL: Public Health Laboratory

PI: Principal Investigator

SAE: serious adverse event

SSL: Secure Sockets Layer

STH: soil-transmitted helminths

WHO: World Health Organization

Synopsis

Study Title	Efficacy and safety of a single-dose regimen and a multi-dose regimen of mebendazole against hookworm infections in children: a randomized controlled trial
Study Type	Phase 4 trial
Indication	Hookworm infection (eggs in stool)
Sample size	180
Investigational Product and Reference Treatment	Mebendazole 100 mg solid tablets 500 mg solid tablets
Protocol Number, Date and Version	14 July 2017, V2.01
Trial registration	Will be registered on (http://www.controlled-trials.com/)
Study Rationale	To provide evidence on the efficacy of a single dose regimen and a multiple dose regimen of mebendazole in children.
Study Objectives	To assess the efficacy and safety of two dose regimens of mebendazole: i) 100 mg solid tablets twice a day for 3 days, and ii) one dose of 500 mg solid tablets of mebendazole in participants aged 6-12, inclusive, infected with hookworm. The primary objective of the trial is to assess the cure rate (CR) of a 3-day regimen of mebendazole against hookworm and a single dose mebendazole treatment. The secondary objectives are to determine if the multi-dose regimen is superior to the single dose regimen, evaluate the efficacy against concomitant soil-transmitted helminth infections, and assess the safety of both mebendazole regimens.
Study -design	Double blind, randomized trial (both participants and outcome assessors are blinded)
Study product intervention	Mebendazole
Comparator(s)	None
Key inclusion / Exclusion criteria	Inclusion: individuals aged between 6 and 12 with a hookworm infection, absence of major systemic illnesses, written informed consent signed by parents/caregivers; and oral assent by the participants. Exclusion: Menarche, any abnormal medical conditions or chronic disease, negative diagnostic result for hookworm, no written informed consent

Primary Endpoints	CR against hookworm
Secondary Endpoints	Egg reduction rate (ERR, based on geometric means) against hookworm, CR/ERR against A. lumbricoides and T. trichiura , safety
Exploratory Endpoints	
 • Sensitivity of Kato Katz compared to quantitative polymerase chain reaction assays • Prevalence of mebendazole genetic resistance markers • Prevalence of STH species
Interim Analyses	None
Study Duration	12 weeks total; up to 8 weeks per participant
Schedule	07/2017 of first-participant in (planned) 10/2017 of last-participant out (planned)
Measurements & procedures	
Two stool samples will be collected if possible on two consecutive days or otherwise within a maximum of 5 days apart. The medical history of the participating individuals will be assessed with a standardized questionnaire, in addition to a clinical examination carried out by the study physician on the treatment day.
 
Randomization of participants into the two treatment arms will be stratified according to intensity of infection. Participants will be interviewed before treatment for clinical symptoms and 3 hours after every morning treatment and 24 hours after every morning treatment about the occurrence of adverse events. The efficacy of the treatment will be determined 14-21 days post-treatment by collecting another two stool samples. All stool samples will be examined with duplicated Kato-Katz thick smears.

Statistical Analyses	
The primary analysis will include all participants with primary end point data (available case analysis). Supplementary, two sensitivity analyses will be conducted imputing all missing endpoint data as treatment failures or all as treatment success. CRs will be calculated as the percentage of egg-positive participants at baseline who become egg-negative after treatment. CRs will be compared by using unadjusted logistic regression. To assess model robustness with respect to covariates, adjusted logistic regressions (adjustment for age, sex, school, weight and strata) will be performed.
 
Geometric and arithmetic mean egg counts will be calculated for the different treatment arms before and after treatment to assess the corresponding ERRs. Bootstrap resampling method with 5,000 replicates will be used to calculate 95% confidence intervals (CIs) for ERRs and the difference of the ERRs.

GCP statement	This study will be conducted in compliance with the protocol, the current version of the Declaration of Helsinki, ICH-GCP E6 as well as all national legal and regulatory requirements.
Key explanation for the inclusion of	This study will be carried out in individuals aged 6-12 years old, since an infection with hookworm and other soil-transmitted

participants	helminths occurs most often in this age group.
Recruitment procedure	The study will be carried out in primary schools in Pemba Island, Tanzania.
Coverage of damages	Winterthur Police Nr. 4746321, National Insurance Cooperation of Tanzania LTD, GTA No: 00062.
Storage of data and samples for future research aims	After the study has been completed all samples will be destroyed and the trial master file will be kept for a minimum of 15 years.
Conflict of interest in relation to the investigated drugs	We declare no conflict of interest in relation to the investigated drugs.
Study site	Public Health Laboratory Ivo de Carneri, Pemba, Tanzania

2. Background information

The most recent estimates suggest that between 600 and 800 million people are infected with one or several of the common soil-transmitted helminths (STHs), which are *A. lumbricoides*, *T. trichiura*, and hookworm [1]. Recently, the global burden due to STHs has been estimated at 3.3 million disability-adjusted life years (DALYs) [2]. The symptoms of STH infections are non-specific and may only be apparent in heavily infected individuals. Children make up the age group which is most at risk of infection with helminths and infections in children are typically the most intense and debilitating [3]. Chronically infected children might suffer from malnutrition, physical and cognitive retardation, and reduced work performance [4].

Currently there are five drugs on the World Health Organization (WHO) model list of essential drugs against STH infections and these drugs have been widely and effectively used [5, 6]. Against *A. lumbricoides*, *T. trichiura* and hookworm infection, the two benzimidazoles (albendazole and mebendazole) are the treatment of choice; the other drugs used against these infections are levamisole and pyrantel pamoate [5-7]. Ivermectin is used to treat *Strongyloides stercoralis* infection, but it is also effective against *A. lumbricoides* infections and moderately effective against *T. trichiura* infection [8, 9]. Both albendazole and mebendazole are used at large scale, within the frame of preventive chemotherapy, which is the regular administration of anthelmintic drugs to at-risk populations (e.g. school-aged children). Preventive chemotherapy is advocated by WHO, because this strategy has a rapid impact on morbidity, and its ease of implementation; the drugs can be administered by personnel outside the health sector (e.g. teacher) independent of recipients body weight, e.g. albendazole or mebendazole are administered at a single oral dose [5].

Mebendazole displays a broad spectrum of activity [6, 10, 11] and it interferes with cellular tubulin formation in the worms' intestine leading to its death [12]. This drug has been extensively used worldwide for more than 30 years both alone and, more recently, in combination with drugs such as praziquantel and ivermectin [13-16]. Mebendazole has shown excellent cure rates (CR) against *A. lumbricoides*. In addition, it reveals low to moderate efficacy against *T. trichiura* and hookworm at single oral doses [6, 17].

Through mass drug administration (MDA) campaigns for STH treatment, hundreds of millions of doses of mebendazole have been distributed worldwide, including to many pregnant women. Multiple studies have failed to find a statistically significant increase in congenital abnormalities among infants born to women exposed to mebendazole during pregnancy as compared to those born to untreated women [55-58]. Over 6,000 women treated with mebendazole are included in these studies, providing more data than for other anthelmintic drugs. Of particular relevance to the proposed trial, a study in Israel found no teratogenic

effects when either a single-dose or a three-day regimen of mebendazole was administered to women in pregnancy, including during the first trimester [57].

The WHO notes in its guidelines on MDA, Preventative chemotherapy in human helminthiasis, that “despite excellent empirical safety profiles, none of the anthelmintic drugs used in MDA campaigns, including mebendazole, is licensed for administration during pregnancy [59]. Nonetheless, risk-benefit analyses show that the advantages of treating women of reproductive age, including those who are pregnant, far outweigh the risks to their health and that of their unborn child.” [60].

WHO notes that using LMP is appropriate for identification of women who are pregnant and to determine the stage of pregnancy. However, among school-age children, defined as those aged 6 to 15 years, the WHO guidance has no requirements for pregnancy testing or screening. The mean age of menarche in Tanzania has been described as 14.3 ± 1.1 years [61], but especially on Zanzibar, the location for this study, there is often a lengthy delay between menarche and sexual activity. The median age of first birth in Zanzibar is 21.7 years and it is clear from demographic surveys that pregnancy is rare among adolescents [62]. The population of Zanzibar is almost entirely Muslim and quite conservative culturally. Sexual activity before marriage is stigmatized and highly discouraged, so testing for pregnancy among 6 to 12 year old girls would be socially inappropriate. As a result, this study proposes to exclude all girls who have started their menses to avoid the possibility of exposure to mebendazole during the first trimester.

Mebendazole can be administered in different doses. The present study will explore the efficacy of the single-dose (500 mg) and the triple-dose (six doses of 100 mg over three consecutive days twice per day) against hookworm. Like albendazole, both regimens of mebendazole (the single- and triple-dose) are included in the National Essential Medicine List for mainland Tanzania [18].

A summary of randomized controlled trials using a single dose of mebendazole (500 mg solid tablets) against hookworm is given in Table 1. The recorded CRs of single-dose mebendazole are very conflicting ranging from 7.6 to 91.1% [19, 20]. Of note, CRs and ERRs of mebendazole observed on Pemba are very low.

Table 1. Randomized-controlled studies which assessed the efficacy of mebendazole (500 mg) against hookworm.

Study	Country	Diagnostic approach	Treatment evaluation	Study design	Age	N	CR	ERR
Abadi 1985 [19]	Indonesia	Kato-Katz and Harada Mori	1-4 wk after treatment	Double-blinded	2-70	45	91.1%	98.3 %

Albonico et al. , 2002 [21]	Tanzania	Kato-Katz	21 d after treatment	Not blinded	9.5 (mean)	424	13.2%	67%
Albonico et al. , 2003 [20]	Tanzania	Kato-Katz	21 d after treatment	Not blinded	7-18	224	7.6%	52.1 %
De Clercq et al. , 1997 [22]	Mali	Kato-Katz	4 wk after treatment	Single-blinded	5-54	35	22.9%	0%
Knopp et al. , 2010 [23]	Tanzania	Kato-Katz	3 wk after treatment	Single-blinded	≥ 5	34	35.3%	78.7 %
Sacko et al. , 1999 [24]	Mali	Kato-Katz	10 d after treatment	Single-blinded	3-70	35	51.4%	68.5 %
Soukhathammavong et al. , 2012 [25]	Laos	Kato-Katz	21-23 d after treatment	Not blinded	6-12	82	17.6%	76.3 %
Speich et al. , 2014 [17]	Tanzania	Kato-Katz	18-23 d after treatment	Double-blinded	6-14	109	17.4%	58.7 %
Steinmann et al. , 2011 [26]	China	Kato-Katz	3-5 wk after treatment	Not blinded	≥ 5	81	31%	83.6 %

We identified 22 studies exploring the efficacy of the triple-dose regimen of mebendazole [27-48]. These studies were conducted between 1973 and 2007 in Asia (N=14), North America (N=1), South America (N=3), Africa (N=2), Europe (N=1) and in the Pacific (N=1) using relatively small samples (average of 40 participants). CRs varied considerably ranging from 30.8% to 100% [36, 37]. Still, the lowest CR of this regimen was considerably higher than the lowest CR of the single-dose regimen CR=7.6%) (Table 1).

The trial presented in this protocol would be, to our knowledge, the first randomized clinical trial comparing the single-dose (500 mg) to the triple-dose (100 mg twice a day for three days) of mebendazole. The fact that the efficacy of the different mebendazole regimens is still highly variable and, therefore, not entirely clear, points to the pressing need to perform further trials to increase evidence. Furthermore, it is important to note that our study will take place in an African setting where the prevalence of hookworm is particularly worrisome and where, up to date, few (2/22) trials testing the efficacy of the multiple dose regimen have taken place. On Pemba, where this trial will take place, the most recent studies have found a prevalence of hookworm ranging from 36 to 97% and the efficacy of a single dose mebendazole is low [17, 49, 50]. Thus, there is a pressing need to develop treatment alternatives. Albendazole is the current standard of care in Pemba for STH treatment; however mebendazole is used in many other settings because of its greater efficacy against infections such as pinworm and Trichinosis. There could be a great public health benefit if an effective mebendazole regimen was identified for the treatment of hookworm in Pemba as the drug would also be effective against numerous other concomitant STH infections.

3. Trial objective and purpose

We hypothesize that both regimens of mebendazole will be effective against hookworm and concomitant soil-transmitted helminths.

The primary objective of the study is to assess the CR (*i.e.* conversion from being egg positive pre-treatment to egg negative post-treatment) of two different mebendazole regimens against hookworm in children (6 - 12 years old): (i) 100 mg of mebendazole twice a day for 3 days and (ii) 500 mg of mebendazole single dose. Thus, the **primary endpoint** of the study is the CR of these two regimens of mebendazole against hookworm.

Additional **secondary endpoints** are (1) the ERR of these two regimens against hookworm, (2) the CR and ERRs of both mebendazole regimens against concomitant soil-transmitted helminth infections, and (3) the safety of both mebendazole regimens. **Exploratory endpoints** include comparison of the sensitivity of Kato Katz to quantitative polymerase chain reaction assays, prevalence of genetic resistance markers among participants, and distribution of hookworm species among participants.

4. Methodology

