4.3. Measure to minimize bias

Study participants eligible for treatment will be randomly assigned to one of the two treatment arms using a computer-generated stratified block randomization code. The random allocation sequence with varying random blocks of four or eight and stratified by 2 levels of baseline infection intensity (light: 1-1999 EPG, and moderate plus heavy: ≥ 2000 EPG hookworm infections) will be provided by a statistician. Both treatment arms will have an equal number of participants with light infection intensity, although the number of light versus moderate/heavy infections are not expected to be equal in each arm, depending on the distribution of infection intensity in the recruited cohort. The codes will be held in a locked cabinet at the Swiss Tropical and Public Health Institute. A copy of this code will be kept in a sealed envelope by one of the co-investigators (will only be unblinded in case there is a serious adverse event, determined by the principal investigator upon consultation with the co-investigators). The blinding will be maintained throughout the trial until data entry and processing are complete and the data have been verified. Following release of the final data, the randomization codes will be released.

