7.1. Definition of primary endpoint

Cure rate of mebendazole against hookworm is the primary endpoint in our study. Since this might be influenced by infection intensity, treatment groups will be equally balanced in terms of infection intensity by 2 levels of baseline infection intensity (light infections and moderate/heavy infections).

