7.2. Justification of number of trial subjects

Sample size calculations for this study are based on the secondary objective comparing the efficacy of the two mebendazole regimens. Based on the published literature with special attention to studies conducted on Pemba Island, we assume that the cure rate of single dose mebendazole against hookworm infections is 20% compared to 40% in the triple treatment regimen [17, 33, 45, 46, 49]. To detect the difference with 80% power at a two-sided 5% significance level we require 79 participants per study arm. To account for potential loss to follow up (which was low in our previous studies in this setting) we aim to recruit in total 180 participants.

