7.3. Description of statistical methods

The primary available case analysis will include all participants with primary end point data. In addition, an intention-to-treat analysis will be conducted considering all participants with missing endpoint data as treatment failure or all as treatment success to ensure that the results are not sensitive to potential loss to follow-up bias. CRs will be calculated as the percentage of egg-positive children at baseline who become egg-negative after treatment. EPG will be assessed by adding up the egg counts from the quadruplicate Kato-Katz thick smears and multiplying this number by a factor of six. The ERR will be calculated as:

$$ERR = 1 - \frac{\frac{1}{n} e^{\sum \log(EPG_{follow-up} + 1)} - 1}{\frac{1}{n} e^{\sum \log(EPG_{baseline} + 1)} - 1}$$

In the primary model we estimate the difference among CRs by using unadjusted logistic regressions. In a subsequent analysis an adjusted logistic regression (adjustment for age, sex, school, weight and strata) will be performed.

Geometric mean egg counts will be calculated for the different treatment arms before and after treatment to assess the corresponding ERRs. Bootstrap resampling method with 5,000 replicates will be used to calculate 95% confidence intervals (CIs) for ERRs and the difference between the ERRs.

Adverse events will be evaluated descriptively as the difference of proportion reporting adverse events before and after treatment.

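### The supportive adjusted hookworm cure-rate model represents infection intensity only by a cut at 2000 EPG, so it adjusts only partly for chance imbalance in baseline egg count

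*Combined protocol and SAP*

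**What the plan says.** - **Primary model (section 7.3).** "In the primary model we estimate the difference among CRs by using unadjusted logistic regressions". It has no intensity term.
- **Adjusted model (synopsis, Statistical Analyses).** "adjusted logistic regressions (adjustment for age, sex, school, weight and strata) will be performed". Section 7.3 lists the same covariates: "an adjusted logistic regression (adjustment for age, sex, school, weight and strata) will be performed". The synopsis gives its purpose as a check of robustness to covariates; section 7.3 places it after the primary model.
- **Strata (section 4.3).** Two levels: "light: 1-1999 EPG, and moderate plus heavy: ≥ 2000 EPG".
- **Eligibility (section 5.2, criterion 4).** At least 100 EPG, so the light stratum in practice runs from 100 to 1999 EPG.
- **Intensity as a predictor (section 7.1).** On cure rate: "Since this might be influenced by infection intensity, treatment groups will be equally balanced in terms of infection intensity by 2 levels".
- **Baseline EPG (section 7.3).** The sum of four slides times six, available for every child. It is used for intensity summaries and the egg reduction rate, but in no cure-rate model.

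**The concern.** The adjusted model is there to show that the comparison of regimens does not depend on covariates. The one predictor of cure that the protocol singles out is infection intensity, and the model sees it only as below or above 2000 EPG. Stratified blocks already balance the arms across that cut. What chance can still unbalance is egg count inside each stratum, mainly the wide light one. A stratum indicator cannot correct that, except so far as age, sex, weight or school happen to track egg count.

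A slope inside the light stratum is plausible from the protocol itself. Section 4.2.2 calls a child negative at follow-up by a rule that includes a fixed limit of 100 EPG. Against that limit a child at 102 EPG needs almost no fall in egg count, while a child at 1998 EPG needs 1 − 100/1998 = 95%. Single-dose egg reduction rates in the Tanzanian rows of Table 1 run from 52.1% to 78.7%. As an illustration, a 60% fall takes 200 EPG to 80 (below the limit) but 1000 EPG to 400 (above it). If the egg-negative status in section 7.3 means zero eggs, this argument weakens and the case rests on section 7.1.

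**Working it through.** **1. The plan's own figure.** Section 7.2: "we assume that the cure rate of single dose mebendazole against hookworm infections is 20% compared to 40% in the triple treatment regimen" and "To detect the difference with 80% power at a two-sided 5% significance level we require 79 participants per study arm". With unpooled variance,

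n = (p₁q₁ + p₂q₂)(z₀.₉₇₅ + z₀.₈₀)² / d² = (0.16 + 0.24) × 7.85 / 0.20² = 78.5, so 79 per arm.

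This reproduces the plan. The 180 recruited give 90 per arm; 1 − 158/180 allows for about 12% loss.

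**2. Width of the light stratum.** 1999/100 = 19.99, a 20-fold range coded as one value.

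**3. Assumptions, because the documents give none.** Baseline EPG is log-normal, truncated at 100, in three versions. The odds ratio (OR) for cure per tenfold higher EPG is 1, 0.5, 0.25 or 0.1. Marginal cure rates are held at 20% and 40%, with blocked allocation within the two strata and 6,000 simulated trials per setting (Monte Carlo SE about 0.5 points per power, smaller for paired differences).

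| Version | Geometric mean EPG | Share ≥ 2000 EPG | Variance of log10 EPG explained by stratum | Variance lying within light stratum |
|---|---|---|---|---|
| A | about 410 | 4% | about 25% | 74% |
| B | about 610 | 13% | about 45% | 52% |
| C | about 960 | 27% | about 60% | 31% |

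**4. Power (%), stratum only → stratum plus log10 EPG.**

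| OR per tenfold EPG | n per arm | A | B | C |
|---|---|---|---|---|
| 1 | 79 | 78.7 → 78.9 | 79.4 → 79.1 | 78.4 → 78.4 |
| 1 | 90 | 83.9 → 83.8 | 84.3 → 84.2 | 83.4 → 83.3 |
| 0.5 | 79 | 79.0 → 79.4 | 79.1 → 79.5 | 79.6 → 80.0 |
| 0.5 | 90 | 83.9 → 84.2 | 85.2 → 85.4 | 84.5 → 84.9 |
| 0.25 | 79 | 79.9 → 81.3 | 81.2 → 82.6 | 80.7 → 82.1 |
| 0.25 | 90 | 84.4 → 85.7 | 84.6 → 86.3 | 85.9 → 87.2 |
| 0.1 | 79 | 79.9 → 83.0 | 80.1 → 84.8 | 82.2 → 86.2 |
| 0.1 | 90 | 84.4 → 87.2 | 85.2 → 88.9 | 87.4 → 90.3 |

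The gains are nil at OR 1, 0.2 to 0.4 points at 0.5, 1.3 to 1.7 at 0.25, and 2.8 to 4.7 at 0.1.

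**5. With the full planned covariate set.** A second simulation used treatment, four other covariates and the stratum, at 90 per arm. Adding log10 EPG gained about 0 / 0.5 / 1–2 / 3–4.5 points at OR 1 / 0.5 / 0.25 / 0.1. The variance of the standardised cure-rate difference changed by about +1% / 0% / −3% / −8%.

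**6. Imbalance left by stratified allocation.** The simulated SD of the between-arm difference in mean log10 EPG is about 0.05. The 95% limit is 1.96 × 0.05 ≈ 0.1, so the ratio of geometric means lies between 10^−0.1 = 0.79 and 10^0.1 = 1.26. The approximate shift in the cure-rate difference at that limit is mean p(1−p) × |ln OR| × 0.1, with mean p(1−p) = (0.16 + 0.24)/2 = 0.20:

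- OR 0.5: 0.20 × 0.693 × 0.1 = 1.4 points
- OR 0.25: 0.20 × 1.386 × 0.1 = 2.8 points
- OR 0.1: 0.20 × 2.303 × 0.1 = 4.6 points

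The planned difference is 20 points.

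**7. Type I error** (OR 0.1, version B, 79 per arm): 4.0% unadjusted, 4.6% with the stratum, 4.5% with stratum and log10 EPG.

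**The case against.** The strongest reply is that the model in question is only supportive. The sample size serves the unadjusted comparison, so nothing done to the adjusted model alters that test. This stands: a reader might infer that the plan throws away power for its main comparison, and the documents do not support that.

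A reader might also infer that protection against imbalance is lost. It is not. Allocation is stratified at 2000 EPG, the adjusted model carries the stratum, and simulated type I error stays below 5%. Mean EPG by arm will also be reported (section 4.2.1), so a large imbalance would be seen. Seeing it is not adjusting for it, though, and a covariate chosen after the imbalance is known is open to challenge.

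Nor can it be said that most of the prognostic information lies inside the light stratum. The within-light share of variance is 31% to 74% over the assumed distributions, so that holds in only part of the range.

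Finally, the extra term is not quite free. About 90 × 0.20 + 90 × 0.40 = 54 cures are expected, and the model would go from six terms to seven, counting one per covariate plus treatment. A stronger covariate also moves the conditional odds ratio further from the marginal one. Step 5 suggests that the cost in precision is about 1% of variance at worst. The change of estimand is met by reporting a standardised difference.

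**Conclusion.** The point holds as a modest weakness of the supportive analysis. The adjusted hookworm model adjusts only partly for egg count, because light infections spanning a 20-fold range share one code while the exact count is already in hand. The gain from adding log10 EPG over stratum adjustment is about 0 to 5 power points. It is nil if intensity does not predict cure, and reaches 3 to 5 only if the odds of cure fall tenfold per tenfold EPG. An imbalance at its 95% limit could shift the cure-rate difference by roughly 1.5 to 5 points over the non-null slopes. All of this rests on assumed EPG distributions and slopes: section 7.1 says only that an influence is possible. Including the stratification factor is accepted practice and is not an error; the continuous term improves on it.

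**What to change.** In the synopsis (Statistical Analyses) and section 7.3, name log10 of baseline hookworm EPG (four-slide sum times six) as a prespecified continuous covariate in the adjusted hookworm cure-rate model, and keep the stratum. No offset is needed, since every eligible child has at least 100 EPG. Report the standardised cure-rate difference beside the conditional odds ratio. If the primary model is ever adjusted for intensity, use the same term there. The cost is one more model term and an assumption of linearity on the log scale, which can be checked; no new data are needed.
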